6.2 TRAINING

Census trainers, antibiotic distributors, hygiene officers, and data collectors will be trained prior to each round.

6.2.1 FIELD STAFF: CENSUS

Field staff will be trained at a two-day workshop immediately before the monitoring visit starts. Field workers will be trained in the use of the electronic data system including the mechanics of the data collection software, the proper handling of the devices, and the charging of the batteries. Before being certified to collect data, census workers must pass a practical examination conducted by the Proctor study coordinator. Field staff will be trained in making the oral antibiotic suspension and completing the study documentation.

6.2.2 FIELD STAFF: SAMPLE COLLECTION

Field staff will be trained at a two-day workshop immediately before the monitoring visit starts. Field staff will receive extensive training in conjunctival swabbing, and we will especially emphasize the danger of contamination of ocular swabs. Several field staff members will be recruited to take conjunctival photographs with a smartphone and 3D printed cellscope. Field staff will only be certified to photograph, or swab if they pass a practical examination conducted by the Proctor study coordinator.

7. MONITORING

We will perform monitoring visits in all study clusters. Monitoring for outcome assessment will occur in the sentinel surveillance development teams for all grappes and will be identical across all study arms.

7.1 OUTCOME MONITORING

Outcome monitoring includes monitoring for all outcomes, including ocular chlamydia prevalence, and clinically active trachoma. Outcome monitoring will occur via an identical protocol for all development teams in all grappes, regardless of randomized study arm. The population-based sample in the sentinel development team will consist of an age-stratified cross-sectional sample at each monitoring visit. Eligibility will be based on the most recent census. We will sample a cross-sectional sample of individuals at each monitoring visit, so that individuals may or may not be sampled at successive visits. We employ this strategy in order to be able to obtain an unbiased population-based estimate of infection and other outcomes at each visit of the trial.

8. EXAMINATION PROCEDURES

8.1 MOBILIZERS

The PNSO study coordinator will hire a community member from each monitored community to mobilize the selected children and ensure a high turnout for the monitoring visits. The person will also select the location for the monitoring visit.

8.2 OUTCOME ASSESSORS

In collaboration with district health officials, the PNSO study coordinator will hire clinical nurses and public health nurses from a neighboring district to perform outcome assessments. The nurses will receive a two-day training session at the beginning of the monitoring visit to review all study procedures. Nurses will be masked to treatment allocation.

8.3 REGISTERING PARTICIPANTS FOR EXAMINATION

Prior to clinical examination the Registration Assistant will identify the participant, verify his/her age, and assign the next random identification number from the randomization list. Random numbers will be assigned for laboratory and database anonymity. This random identification number will be entered into a tablet computer in order to link the laboratory specimens with the unique identification number used for the study.

8.4 GLOVING OF THE EXAMINERS HANDS

Any hand that will touch a participant's face or eyelids must be gloved for the examination. The examiner will put latex gloves on both of their hands prior to touching the participants' eyelid, and a new pair of gloves will be used for each participant. Purell® Instant Hand Sanitizer will be available for hand sanitization.

8.5 EXAMINATION POSITIONS

[figure not shown]
The examining position to be used in the field for young children will be the classic pediatric ophthalmic examination technique. With the aid of a helper seated directly opposite the examiner, the child will be positioned with his/her head between the examiner's knees, with the child's face looking upwards towards the examiner. The legs of the child will be

straddled across the helper and the arms held gently across the child's chest. Care should be taken to keep the child's eyes above the level of the examiner's knees, in order to properly take the conjunctival swab.

For examining older children, the participant should stand or sit facing the seated examiner, such that the participant's eyes are at the examiner's eye level.

8.6 FIELD SPECIMEN COLLECTION QUALITY CONTROL MEASURES

The stations for examination and swabbing of participants are displayed below. This setup is designed for the most efficient patient flow and to minimize errors or confusion between team members. This diagram shows the station configuration for a four-person team.

8.7 CONJUNCTIVAL SWAB COLLECTION

A random sample of 50 children <10 years old will undergo conjunctival swabbing at 0 and 36 months. Swabs will be processed for *C. trachomatis*. Samples will be processed within in pools of 5. Any positive pools will be unpooled and processed individually. Swabs will be labeled with a unique barcode in the field, which will link to a unique identification number. The number will be linked with the individual's census entry during swab collections in the field.

8.7.1 PROTOCOL FOR COLLECTION

After clinical photography and grading, we will collect 2 conjunctival swabs per child. One conjunctival swab will be stored in Zymo's DNA/RNA Shield media, and one will be stored dry. The examiner will swab the upper right conjunctiva while it is still everted as follows:

1. Pull apart the swab sachet in a sterile manner to reveal only the tip of the swab shaft with the swab head still remaining sterile deep in the sachet.
2. Pull out the swab and hold it no closer than 1 inch from the tip of the swab in order to avoid contamination.
3. Run the swab firmly on the upper tarsal conjunctiva in one direction.
4. Rotate the swab 120° along its axis and rub firmly again. Rotate and repeat a third time.

Materials Needed.

Swabs: Specimens will be collected using sterile, individually-wrapped Dacron polyester-tipped swabs with a plastic shaft (manufactured by Fisherbrand®).

Sample Tubes: All field samples for DNA testing will be collected into sterile DNA-free 2.0ml microcentrifuge tubes, manufactured by Sarstedt®.

Cooler Bags with Frozen Ice Packs: Same as samples for resistance testing.

-20°C Freezer

Protocol for Tubing and Handling of Conjunctival Samples. The swab shaft should only be inserted until the Dacron swab head is fully in the tube. The tuber should lower the cap onto the swab shaft held by the examiner, and the examiner should quickly break the swab shaft using a swift downward snapping wrist movement (this will be demonstrated in the field the first day).

All samples will be in sample boxes, labeled with the village name for easy future identification.

- Study name and visit number: ARRET 0
- Where were samples collected: Village name
- How many samples were collected: Number of swabs and circle the number
- When were samples collected: Date (19SEP2019)
- What type of samples were collected: Dry conj or Zymo conj

Negative Field Controls. Four negative field control swabs will be taken in each community to assess for contamination. Two control swabs are taken before specimen collection begins in a community (one dry, one in Zymo media); and again upon completion of specimen collection (one dry, one in Zymo media).

1. For each negative field control, the examiner will open a new swab as described above.
2. Wave the swab in the air, without making contact with anyone/anything.
3. At the beginning of the day, tube one conjunctival swab in Zymo media, and tube one in an empty, dry tube, following the protocol above.
4. At the end of the day, tube one conjunctival swab in Zymo media, and tube one in an empty, dry tube, following the protocol above.

8.8 FIELD GRADING AND CLINICAL PHOTOGRAPHY

The same random sample of 50 children <10 years old who will undergo conjunctival swabbing will also undergo conjunctival photography and trachoma field grading. Four specific team members will be designated as photographers for the entire trial to ensure high quality photographs by an experienced photographer.

8.8.1 TRACHOMA FIELD GRADING OF THE CONJUNCTIVA

Trachoma field grading will be performed in addition to the conjunctival photography. Field grading will be done before photography or swabbing.

8.8.2 TRACHOMA FIELD GRADING PROTOCOL

First, the examiner will wear the loup and will flip the conjunctiva.

The examiner will flip the child's **right** eyelid:

1. Wearing gloves, the examiner will use his or her fingers to grasp the central part of the child's right upper eyelid.
2. The eyelid is then turned over using the finger of another hand (or the tip of a sterile swab) as a fulcrum.
3. The inverted eyelid is held in place by the examiner's non-dominant hand

The examiner will observe the conjunctiva and will tell the photographer the trachoma grading he found following the WHO simplified trachoma grading scale below

TF: trachomatous follicular	Presence of five or more follicles in the upper tarsal conjunctiva
TI: Trachomatous Inflammation	Pronounced inflammatory thickening of the upper tarsal conjunctiva
TS: Trachomatous scarring	The presence of scarring in the tarsal conjunctiva
TT: trachomatous trichiasis	At least one eyelash rubs on the eyeball
CO: corneal opacity	Easily visible corneal opacity

This grading will be recorded in the mobile application.

8.8.3 CLINICAL PHOTOGRAPHY OF THE CONJUNCTIVA

The photographer will take photographs of the conjunctiva with a handheld smartphone with a 3D-printed cellscope. Conjunctival photography causes no damage to the eye, is well tolerated by children, and is a standard clinical procedure at UCSF. We will use an identical protocol to that being used in the MORDOR study. Clinical photography will be performed before conjunctival swabbing and after field grading. Photographs will be identified by first taking a photograph of the 6-digit random identification sticker that was assigned to the child during the registration phase of the study visit. By convention, all photographs taken after this random number (up to the next photographed random number) belong to the preceding random number. If a random number is mistakenly not photographed before taking a photograph of the conjunctiva, it may be photographed afterwards; in this case, a note should be included that says “preceding photos”. Photographs are taken in the mobile application.

8.8.4 PHOTOGRAPHY PROTOCOL

Equipment needed. Smartphone, 3D-printed cell scope and battery, latex or other sterile gloves

Photograph Procedures.

1. Place the participant into position that will allow maximum stability; standing, sitting, or “head-clamp” position. Employing a village volunteer to help is very useful.
2. The photographer scans the child’s bracelet using the smartphone.
3. The examiner everts the child’s right upper eyelid.
 - a. Wearing latex (or other sterile) gloves, the examiner will use his/her fingertips to grasp the central portion of the participant's right upper lid eyelashes.
 - b. The right upper lid is then everted, using a finger of the examiner's other hand (or the end of a sterile swab) as a fulcrum, positioned superior to the tarsal plate.
 - c. The everted lid is held in place by the examiner's non-dominant hand, holding the eyelashes against the orbital rim, thus keeping the examiner's dominant hand free for swabbing the tarsal conjunctiva. If the right eyelid is difficult to flip because of eye disease or injury, the examiner is allowed to flip the left eyelid instead.
4. The examiner holds the child’s flipped eyelid for the photographer.

5. Take a minimum of two photos. If there is any doubt about the quality of the photo while the participant is in position it is better to continue to take more photographs before the participant is allowed to leave. It is easy to delete photos if they are not needed.
6. Check photos before allowing the child to leave. If they are not acceptable, repeat the procedure. Only stop if the participant or guardian requests that we stop, or if it is deemed impossible, even with further attempts. Note that we have obtained >95% acceptance in previous studies.
7. If the child cannot be photographed for some reason, it does not affect the eligibility of the child.

Smartphone

Cellscope

**The conjunctiva should take up the majority of the space
in the center of the photograph.**

- Conjunctiva is completely everted
- Conjunctiva is centered
- In Focus: If there are blood vessels, they should be focused.
- Entire conjunctiva: Make sure the examiner's glove is not covering part of the everted conjunctiva
- Appropriate brightness: Not too bright and not too dark; no sun in the background

Taking Photographs of the Conjunctiva.

When the examiner has the child's upper eyelid everted:

- Turn on the LED light on the Cellscope
- Activate the camera
- To take a photo of the conjunctiva:
- If necessary, tap the center button to focus
- Remember to turn off the LED light after taking photographs to save battery power.

After photographs are taken, disinfect the part of the cellscope that touches the child's face with an alcohol wipe.

Photo requirement: Take at least two good conjunctival photographs.

8.8.5 GRADING OF CLINICAL CONJUNCTIVAL PHOTOS

Three experienced ophthalmologists will grade the photographs, masked to treatment allocation. We will present graders an ordered set of photographs for each monitored individual, with the study visit identified for each photograph (e.g., baseline or 36 months). Graders will grade each photograph in the set for follicles and inflammation according to the grading scale described by the WHO Simplified Grading System.

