4.3 MASKING

Given the nature of the intervention, participants and investigators will not be masked as to study arm. Census workers who conduct the census will be masked to treatment arm of the study community, as will outcome assessors conducting clinical examinations and collecting swabs. Laboratory personnel processing conjunctival swabs for ocular chlamydia and dried blood spots for serology will be masked to treatment group and to control versus study samples. Photographs will be graded by a masked grader. All samples and photographs will be processed in a random order. Masking will not only minimize bias introduced through knowledge of treatment assignment but will ensure that the census and outcome assessment is identical in all study communities.

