8.8.6 PHOTOGRAPHIC READING CENTER

The Reading Center for grading of conjunctival photographs will be based at the Proctor Foundation. Three graders will independently grade each photograph, masked to treatment allocation. We will choose the consensus or median grade for all outcomes. We will assess inter- and intra-observer agreement with kappa statistics.

Facility/Equipment. A dedicated room with a single 24" computer monitor (1920 x 1200 pixels, re-calibrated monthly to a color temperature of 6500 Kelvin and 2.2 gamma) will be used to grade photographs. Full-screen photographs will be read at 26 inches with the shades drawn and lights off.

Naming Conventions. The PNSO study coordinator will be responsible for renaming each of the photographs taken during the study. The naming convention to be used is that the file will be a concatenation of the 6-digit random number, then the study visit (0, 36), and then the photograph number from that visit. For example, if a child with random number 111999 had 3 photographs taken at the 36-month visit, these 3 photographs would be relabeled as 111999-36-1, 111999-36-2, and 111999-36-3.

Photograph Selection and Arrangement. The best quality conjunctival photograph will be selected from each participant and displayed in a PowerPoint slide (left=month 0; right=month 36). The random number will be added to each PowerPoint slide for identification purposes. The best photograph will be pre-selected but the photographic graders will have access to all other photographs taken of the study participant in a folder on the computer; they simply navigate to the correct file name using the naming conventions listed above.

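### Photographs are to be graded as visit-labelled month 0 / month 36 sets, a layout that suits a cohort rather than repeated cross-sectional samples and leaves photographic TF/TI open to avoidable visit-expectation bias

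*Protocol*

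**What the plan says.** On presentation to graders, Protocol 8.8.5 says "We will present graders an ordered set of photographs for each monitored individual, with the study visit identified for each photograph". Section 8.8.6 has the best photograph of each participant "displayed in a PowerPoint slide (left=month 0; right=month 36"), adds one random number to the slide, and builds each file name from the random number, the visit (0 or 36) and a photograph number. Graders can open a child's other photographs by file name, so they see the visit there too.

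On masking, 8.8.5 says "Three experienced ophthalmologists will grade the photographs, masked to treatment allocation". Neither 8.8.5 nor 8.8.6 masks graders to visit. Protocol 4.3 says "All samples and photographs will be processed in a random order".

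On sampling, Protocol 7.1 says "We will sample a cross-sectional sample of individuals at each monitoring visit, so that individuals may or may not be sampled at successive visits". SAP 3.7 and 5.4 likewise describe repeated cross-sectional surveys at baseline and 36 months. At registration, Protocol 8.3 has staff "assign the next random identification number from the randomization list".

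On use, SAP 6.2.1 (Aim 1) turns photographic TF and TI into community-level averages and analyses them as it does the primary outcome, adjusting for baseline. SAP 3.4 places secondary outcomes in the noninferiority framework.

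**The concern.** An ordered, visit-labelled set per child is a cohort procedure. In this trial many children may be photographed once only. A child with two photographs would be graded side by side with a known time order; a child with one would be graded alone. The plan gives no specific instruction for the second case.

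Three things are at stake, all in secondary outcomes:

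- A grader who knows the visit may expect decline. SAP 2.1 itself raises the possibility that trachoma is disappearing through secular trends. That expectation can move TF/TI levels and the apparent change from baseline.
- Side-by-side grading makes a child's two grades depend on each other.
- If the effect is to pull month-36 grades toward a common expectation, the arm difference shrinks. In a noninferiority comparison, shrinkage favours a finding of noninferiority even when it acts on both arms equally.

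**Working it through.** **1. The plan's own TF figure.** SAP 3.3.1 assumes a between-community SD of 0.05 and a correlation of 0.5. Residual SD = 0.05 × √(1 − 0.5²) = 0.0433. With 40 communities per arm, two-sided 5% and 80% power, margin = (1.960 + 0.842) × 0.0433 × √(2/40) = 0.027. This agrees, after rounding, with the stated margin of approximately 3%. The present point disputes no figure in the plan.

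**2. Share of a month-36 sample with a baseline photograph.**

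Formula: share = s × min(1, 50/C), with C = a × (residents in the frame).

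Inputs from the documents:
- 50 children aged 0-9 photographed per community at each visit (Protocol 4.1.2 and 8.8).
- Communities of 200 to 2,000 residents (Protocol 2.3.1; SAP 5.2).

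Assumptions not in the documents:
- a, the proportion of residents aged 0-9: 0.30 to 0.40.
- s, the proportion of the month-36 sample that was in the baseline frame: 0.70 to 0.75. Children aged 3-9 at month 36 were alive at baseline; evenly spread ages give 7/10.
- The whole grappe is the frame, with no migration or death.

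| Residents | C (a = 0.30 to 0.40) | Highest share (a = 0.30, s = 0.75) | Lowest share (a = 0.40, s = 0.70) |
|---|---|---|---|
| 200 | 60 to 80 | 0.75 × 50/60 = 63% | 0.70 × 50/80 = 44% |
| 500 | 150 to 200 | 0.75 × 50/150 = 25% | 0.70 × 50/200 = 18% |
| 1,000 | 300 to 400 | 0.75 × 50/300 = 13% | 0.70 × 50/400 = 9% |
| 2,000 | 600 to 800 | 0.75 × 50/600 = 6% | 0.70 × 50/800 = 4% |

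**3. If the frame is smaller.** Protocol 4.2.2, 7 and 7.1 place monitoring in a sentinel development team within the grappe and do not give its size. More than half of a month-36 sample is paired once C falls below 50 × 0.70/0.5 = 70 children (or 75 at s = 0.75). For a frame of 150 residents with a = 0.35 and s = 0.70, the share is 0.70 × 50/52.5 = 67%. The share cannot exceed s, because children under 3 at month 36 were born after baseline. So some 25-30% of the month-36 sample lacks a pair even in the smallest frame.

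**4. Matching of the photographs that do pair.** Under Protocol 8.3 a child sampled twice may receive two random numbers, while the 8.8.6 slide carries one and files are named by it. File names alone may therefore fail to match. The tablet entry in 8.3 and the census link in 14.1.2 could join them through the study identifier, but 8.8.6 does not call for that step.

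**5. What shrinkage would do, as illustration only.** The standard error of the TF difference is 0.0433 × √(2/40) = 0.0097. If a true 3-point difference were read as 2.7 or 2.4 points, the chance of wrongly declaring TF noninferior would be Φ(0.003/0.0097 − 1.96) = 4.9% or Φ(0.006/0.0097 − 1.96) = 9.0%, against 2.5% with no shrinkage. The factors 0.9 and 0.8 are invented to show direction; the documents give no basis for them.

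**The case against.** Much can be said for the plan. Graders are masked to arm, so knowing the visit acts on both arms alike and favours neither by itself. Three graders work independently, a consensus or median grade is taken, and agreement is assessed by kappa. Any variation of grading conditions with community size is balanced between arms in expectation by randomization. Change over time is not an Aim 1 estimand: the SAP compares arms at 36 months with baseline as a covariate. A child seen once can simply be treated as a set from one visit. All of this stands, and it limits the point to secondary outcomes. It does not remove it, because a consensus of three graders does not correct an expectation that all three share.

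A reader might also infer stronger conclusions that the documents do not support:

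- *Most children have no pair.* This holds for whole grappes of moderate or large size, but the size of the sentinel team is not stated.
- *Files will not pair.* The documents do not say whether a returning child keeps a number, and the census identifier could link the records.
- *The grading rule flatly contradicts Protocol 4.3.* Random order may mean the order of children, with visits ordered within a child. Even then the visit is disclosed.
- *Aim 2 is affected.* The Aim 2 section of the SAP does not say whether its TF and TI are photographic or field grades, and field grades are also collected (Protocol 8.8.1-8.8.2).

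**Conclusion.** The point holds as a recommended change for secondary outcomes. What is on the page is that graders see the visit, that the layout presumes a child photographed twice, and that this fits poorly with the sampling in Protocol 7.1 and the random order in 4.3. How many children would be paired cannot be settled from the documents. With the whole grappe as frame it runs from about 44-63% of a month-36 sample at 200 residents to 4-6% at 2,000, on the assumed values of a and s; a small sentinel team would raise it.

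The size of any bias is unknown. It can distort photographic TF/TI levels and change over time and may shrink the arm difference. It reaches Aim 2 only if photographic grades are used there. The arm masking, the primary PCR outcome, the sample size and the stated margins are unaffected.

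**What to change.** In Protocol 8.8.5 and 8.8.6, replace the ordered, left/right presentation with single photographs graded in one random order across visits, communities and arms. Remove the visit from the slides and from the file names that graders see; a neutral grading number linked in the database is enough. Place a random set of repeats in the same queue, so that the planned intra-observer kappa has a defined source. Sections 4.3, 7.1, 8.8.5 and 8.8.6 then agree, and no rule for unpaired children is needed.

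The cost is protocol wording, a shuffled file list and a little extra grading for the repeats, with the same three graders. No analysis is lost, because the SAP uses community prevalence at each visit. The one downside is that baseline photographs are graded with the month-36 set, so photographic TF/TI are not available early. SAP 3.5 plans no interim efficacy or futility analysis, and field grades from baseline remain available in the meantime.
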